5. TEST ARTICLE ALLOCATION AND MASKING

5.1. Test Article Allocation

The study lenses will be worn in a bilateral and random fashion using a 2×2 crossover design. A computer-generated randomization scheme will be used to randomly assign subjects to one of the two possible lens wear sequences: Test/Control or Control/Test. The random scheme

will be generated using the PROC PLAN procedure from Statistical Analysis System (SAS) Software Version 9.4 or higher (SAS Institute, Cary, NC).⁶

Randomization will be performed at the first visit prior to the first fitting. The following must have occurred prior to randomization:

- Informed consent must have been obtained.
- The subject must have met all eligibility criteria.
- The subject's screening and baseline information must have been collected.

When dispensing test articles, the following steps should be followed to maintain randomization codes:

- 1. Investigator or designee (documented on the Delegation Log) will consult the lens fitting schedule to obtain the test article assignment for that subject prior to dispensing.
- 2. Investigator or designee will record the subject's number on the appropriate line of the lens fitting schedule.
- 3. Investigator or designee will pull the appropriate test articles from the study supply. All test articles that are opened, whether dispensed (placed/fit on eye or dispensed outside the clinical site) or not, must be recorded on the Test Article Accountability Log in the "Dispensed" section.

5.2. Masking

Due to differences in cosmetic pattern between the Test and Control lenses, subjects in this study cannot be double-masked. However, subjects, investigators, and clinical site personnel will be unaware of the identity (brand) of both study lenses.

Under normal circumstances, the mask should not be broken until all subjects have completed the study and the database are finalized. Otherwise, the mask should be broken only if specific emergency treatment/course of action would be dictated by knowing the identity of the treatment. In such cases, the Investigator may, in an emergency, must contact the medical monitor. In the event the mask is broken, the Sponsor must be informed as soon as possible. The date, time, and reason for the unmasking must be documented in the subject record.

5.3. Procedures for Maintaining and Breaking the Masking

The identity of the test article shall not be broken unless information concerning the identity of the study lenses is necessary for the urgent medical treatment of a subject. The Sponsor must be notified as soon as possible if mask is broken.

If the masked need to be broken, the site investigatory or clinical site personnel designee will pull the appropriate test articles from the study supply. All test articles opened, whether dispensed (placed/fit on eye or dispensed outside the clinical site) or not, must be record on the Test Article Accountability Log in the "Dispensed" section.

6. STUDY INTERVENTION

6.1. Identity of Test Articles

The following contact lenses will be used in this study:

1	Control	Test
Name	1-Day ACUVUE	Investigational
	Define – Fresh Honey	etafilcon A daily
		disposable cosmetic
		lens
Manufacturer	Johnson & Johnson	Johnson & Johnson
Lens Material	etafilcon A	etafilcon A
Nominal Base	8.5 mm	8.5 mm
Curve @ 22°C		
Nominal	14.2 mm	14.2 mm
Diameter @		
22°C		
Nominal	-1.00 to -6.00 D	-1.00 to -6.00 D
Distance Powers		
(D)		
Modality in	Daily	Daily
Current Study	2100	
Replacement	Daily	Daily
Frequency	2/079	
Packaging Form	Blister	Blister
(vial, blister,		
etc.)		

Table 1: Test Article

Each subject will wear approximately 12 of each lens type.

6.2. Ancillary Supplies/Products

The following solutions will be used in this study:

Sensitive Eyes Plus (Bausch & Lomb) or country-specific alternative approved by the sponsor, FluStrips (Contacare) or country-specific alternative approved by the sponsor, and Tears Naturale Free (Alcon) or country-specific alternative approved by the sponsor.

Table 2: Ancillary Supplies

		Solution	
	Sensitive Eyes plus Saline (or	Tears Naturale Free (or other	FluStrips Fluorescein (or
Solution Name/Description	other sponsor- approved	sponsor- approved	other sponsor- approved
	product)	product)	product)
Manufacturer	Bausch & Lomb	Alcon	Contacare Ophthalmics Diagnostics (EOU)
Preservative	None	None	None
Other distinguishing items (dye, packaging, approval status, etc.	NA	NA	D&C Yellow No. 8, 0.6 mg

6.3. Administration of Test Articles

Test articles will be dispensed to subjects meeting all eligibility requirements, including any dispensing requirements set forth in this clinical protocol. Subjects will be dispensed an adequate supply of test articles to complete the study. Lost or damaged test articles may be replaced at the discretion of the investigator and/or the sponsor.

6.4. Packaging and Labeling

The test articles will be packaged in blisters as the primary packaging. The test articles will be over-labeled to mask the subject and investigators to the identity of the lens. The test articles will be in plastic bags as the secondary packaging form. The sample study label is shown below:

6.5. Storage Conditions

Test articles will be maintained at ambient temperatures at the clinical site. Test articles must be kept under secure conditions.

6.6. Collection and Storage of Samples

No samples will be collected as part of the study procedures.

When possible, any lens or test article associated with an Adverse Event and/or a Product Quality Complaint must be retained and stored in a glass vial with moderate solution pending directions from the sponsor for potential return to JJVC.

6.7. Accountability of Test Articles

JJVC will provide the Investigator with sufficient quantities of study articles and supplies to complete the investigation. The Investigator is asked to retain all lens shipment documentation for the test article accountability records.

Test articles must be kept in a locked storage cabinet, accessible only to those assigned by the Investigator for dispensing. The Investigator may delegate this activity to authorized study site personnel listed on the Site Delegation Log. All test articles must be accounted. This includes:

- 1. What was dispensed for the subject for trial fitting, to wear out of the office, or issued for the subject to replace appropriately between visits.
- 2. What was returned to the Investigator unused, including expired or malfunctioning product.
- 3. The number and reason for unplanned replacements.

The Investigator will collect all unused test articles from the subjects at the end of the subject's participation. Subject returned unused test articles must be separated from the clinical study inventory of un-dispensed test articles and must be labeled with the subject number and date of return. Following final reconciliation of test articles by the monitor, the Investigator or monitor will destroy all unused test articles per sponsor approved method.

If there is a discrepancy between the shipment documents and the contents, contact the study monitor immediately.

7. STUDY EVALUATIONS

7.1. Time and Event Schedule

Table 3: Time and Events

Visit Information	Visit 1	Visit 2	Washout	Visit 3	Visit 4
	Screening,	Treatment		Dispense	Treatment
	Baseline,	1 Follow-		Treatment	2 Follow-
	Dispense	up,		2	up,
	Treatment	Washout		_	Final
	1				Evaluation
Time Point	Day 0	6±1	2 - 5	2-5 days	Day 6 ± 1
		days from	days	from V2	days from
		V1			V3
Estimated Visit Duration	2 hours	1 hour		1 hour	1 hour
Study Informed Consent	X				
Inclusion/Exclusion	X				
Screening Criteria					
Demographics	X				
Medical History &	X	X		Х	Х
medication review				20000000	
Habitual Lens Info	X				
CLUE Baseline	X				
HVID	X				
Keratometry	X				
Entrance/Exit VA	X	X		X	X
Subjective Refraction	X				
Biomicroscopy	X	X		Х	X
Subject Reported Ocular	X	X		Х	Х
Symptoms	1200000			Dis Andreaders a	
Eligibility after baseline	X				
exam					
Randomization	X				
Lens Fitting #1	X				
Lens Fitting #2				Х	
Over-	X			Х	
refraction/optimization	2010/00			0.0000	
CLUE Post-Fit	X			Х	
CLUE Follow-Up		X			Х
logMAR VA	X			Х	
Cosmetic Lens Fit	X	Х		Х	Х
Assessment	0		1		
Hula Hoop Assessment	Х	Х		Х	X
Lens Fit Assessment	X	Х		Х	Х
Wettability Characteristics	X	Х		Х	Х

Visit Information	Visit 1	Visit 2	Washout	Visit 3	Visit 4
	Screening,	Treatment		Dispense	Treatment
	Baseline,	1 Follow-		Treatment	2 Follow-
	Dispense	up,		2	up,
	Treatment	Washout			Final
	1		,		Evaluation
Time Point	Day 0	6 ± 1	2 - 5	2-5 days	Day 6 ± 1
		days from	days	from V2	days from
		V1			V3
Estimated Visit Duration	2 hours	1 hour		1 hour	1 hour
Lens Surface/Deposits	X	X		X	X
Assessment					
Lens Dispensing &	X			X	
Instruction	0 4				
Washout instructions		X			
Adverse Event Review		X		Х	Х
Final Evaluation					Х

7.2. Detailed Study Procedures

VISIT 1

The subjects must present to Visit 1 wearing their habitual contact lenses.

	Visit 1: Screening			
Step	Procedure	Details		
1.1	Statement of Informed Consent	Each subject must read, understand, and sign the Statement of Informed Consent before being enrolled into the study. The Principal Investigator or his/her designee conducting the informed consent discussion must also sign the consent form. Note : The subject must be provided a signed copy of this document.		
1.2	Demographics	Record the subject's year of birth, gender, race and ethnicity.		
1.3	Asian Eye Characteristics	Confirm if the subject meets the criteria listed in Appendix C.	Appendix D	
1.4	Medical History and Concomitant Medications	Questions regarding the subjects' medical history and concomitant medications.		
1.5	Habitual Lenses	Questions regarding the subject's habitual lens type, parameters, wear schedule and duration.		

	Visit 1: Screening				
Step	Procedure	Details			
1.6	Wear time and Comfortable Wear Time with Habitual Lenses	Record the subject's wear time and comfortable wear time with their habitual contact lenses.			
1.7	Eligibility after Screening	All responses to Screening Inclusion Criteria questions must be answered "yes" and all responses to Exclusion Criteria must be answered "no" for the subject to be considered eligible. If subject is deemed to be ineligible after screening, proceed to Final Evaluation and complete Subject Disposition. Visual Acuity,			
		Refraction and Biomicroscopy forms are not required.			

	Visit 1: Baseline			
Step	Procedure	Details		
1.8	CLUE Baseline Questionnaire	The subject will respond to the PRO Baseline CLUE Questionnaire	Appendix A	
1.9	Entrance Visual Acuity	Record the distance Snellen visual acuity (OD, OS, and OU) to the nearest letter with their habitual contact lens correction in place. Subjects must read the smallest line until at least 50% of the letters are read incorrectly.		
1.10	Remove Habitual Contact Lenses	The subject's habitual lenses will be removed and stored in their own lens case. If they forgot to bring their lens case, one will be provided to them.		
1.11	Iris Color	Record iris color in both eyes (self-reported)		
1.12	Horizontal visible iris diameter (HVID)	Measure the horizontal visible iris diameter for each eye separately using a pd stick in normal room illumination. Measure from the edge of the iris nasally to the edge of the iris temporally. Record in mm to one decimal place.		
1.13	Keratometry	Record the keratometry readings OD and OS.		

	Visit 1: Baseline				
Step	Procedure	Details			
1.14	Subjective Sphero- cylindrical Refraction	Complete subjective spherocylindrical refraction and record the resultant distance visual acuity (OD, OS and OU) to the nearest letter. Note: The subjects contact lens powers based on the vertexed (12 mm), spherical equivalent must be between -1.00 and -6.00 D.			
1.15	Slit Lamp Findings	 FDA Slit Lamp Classification Scale will be used to grade the findings and determine eligibility. If any slit lamp findings are Grade 3 or higher, the subject is ineligible to continue. Continue to the Final Evaluation Form and dismiss the subject. If the clearance of the fluorescein needs to be expedited, preservative-free rewetting drops or saline may be instilled. 			
1.16	Eligibility after Baseline	All responses to Inclusion Criteria questions must be answered "yes" and all responses to Exclusion Criteria questions must be answered "no" for the subject to be considered eligible.			

	Visit 1: Treatment 1 Lens Fitting			
Step	Procedure	Details		
1.17	Lens Selection	Assign the study lens based on the randomization scheme. Select the contact lens power based on the vertexed (12 mm), spherical equivalent subjective refraction.		
1.18	Lens Insertion	The Subject inserts the study lenses. Record the time of lens insertion. Check for lens damage under the slit lamp before proceeding with lens settling. Replace damaged lenses if applicable. Note: Designated site staff should observe the insertion process. If it appears that the subject attempts to insert a lens that is "inside-out", they should interfere to avoid incorrect insertion.		

	Visit 1: Treatment 1 Lens Fitting			
Step	Procedure	Details		
		Note 2: If the lens moves excessively on the eye after insertion, ask the subject to remove the lens, confirm lens is not inverted (correct if it is) and reinsert.		
1.19	Lens Settling	Allow the study lenses to settle for a minimum of 5 minutes.		
1.20	Subjective Best Sphere Over Refraction	Perform subjective best sphere refraction over the study lenses with a phoropter (adopt the maximum plus to maximum visual acuity (MPMVA) approach and use the duo-chrome test for binocular balancing) and record the best corrected distance visual acuity to the nearest letter (OD, OS, OU).		
1.21	Lens Power Modification (if applicable)	Adjust the lens power if the subject's best sphere over-refraction is not plano. For each power modification, repeat steps (1.16 to 1.19). Two power modifications are allowed.		
1.22	Visual Acuity	Record the distance Snellen visual acuity (OD, OS, and OU) to the nearest letter with the study contact lens correction in place. Subjects must read the smallest line until at least 50% of the letters are read incorrectly.		
1.23	Distance ETDRS logMAR Visual Acuity	 Per, please confirm room illuminance and chart luminance acceptable ranges for both high/low contrast visual acuity testing. 1. Under high illumination and high chart luminance, record the distance (4 meter) ETDRS high contrast visual acuity twice OD (HC1-HC2) and twice OS (HC3-HC4). 		
		 Under high illumination and high chart luminance, record the distance (4 meter) ETDRS low contrast visual acuity twice OD (LC1-LC2) and twice OS (LC3- LC4). With the goggles on, under normal illumination and chart luminance, record the distance (4 meter) ETDRS high contrast visual acuity twice OD 		

	Visit 1: Treatment 1 Lens Fitting			
Step	Procedure	Details		
		(HC5-HC6 and twice OS (HC7-HC8).Allow subject to adjust to dim condition for 3 minutes.Letter-by-letter results will be recorded into		
		the electronic data capture form, which will calculate the visual performance score for each chart read.		
1.24	Subject Reported Ocular Symptoms	Subjects will respond to a verbal open-ended symptoms questionnaire.		
1.25	CLUE Post-Fit Questionnaire	The subject will respond to the CLUE Post- Fit Questionnaire	, Appendix A	
1.26	Cosmetic Lens Fit Assessment (without slit-lamp)	The Cosmetic Lens Assessment will be assessed by the investigator (without slit- lamp) in primary gaze and extreme gaze (right, left, and upgaze) at a normal conversation distance (approximately three (3) feet away from the subject).	Appendix E	
1.27	Hula Hoop Assessment (without slit-lamp) *If unacceptable cosmetic fit in any gaze.*	If there is an unacceptable cosmetic fit in any gaze, the Hula Hoop Assessment will be assessed by the investigator (without slit- lamp) in primary gaze and extreme gaze (right, left, and upgaze) at a normal conversation distance (approximately three (3) feet away from the subject).	Appendix E	
1.28	Subjective Lens Fit Assessment	 Evaluate overall lens fit acceptance (acceptable or unacceptable) based on centration, movement and other fitting characteristics. An unacceptable fit is deemed by one of the following criteria: Presence of limbal exposure (appearance of clear cornea) in any gaze; Presence of edge lift; Presence of unacceptable movement (excessive or insufficient) in all three of the following conditions: primary gaze, up gaze, and tightness on push up. 		

		Visit 1: Treatment 1 Lens Fitting	
Step	Procedure	Details	
2774		Note: if lens fit is unacceptable subject will	_
		be discontinued from the study.	
1.29	Wettability	Record the white light lens wettability of both	
	Characteristics	lenses.	
1.30	Surface Deposits	Record any front and back surface lens	
1.01		deposits.	
1.31	Continuance	For the subject to continue in the study, they	
		must meet all three of the following criteria:	
		 Visual acuity is 20/30 or better OD and OS 	
		• The lens fit is acceptable OD and OS	
		Investigator approval. If the Investigator does not approve the	
		dispensing of the first study lens, then	
		the study is terminated for that	
		subject.	
1.32	Dispense	The lenses will be dispensed for a 5 to 7 day	
		wearing period. During this time, they are	
		required to wear the lenses at least 6 hours	
		per day.	
		 Dispense enough lenses to last the 	
		subject to their scheduled follow-up	
		visit. Do not dispense extras*.	
		The lenses will be worn as daily	
		wear/daily disposable only.	
		Rewetting drops are permitted if	
		needed.	
		• A patient instruction booklet will be	
		provided.	
		• Subjects will be scheduled for their 5-	
		7-day follow-up visit, ensuring that they wear the study lens at least 6	
		hours on the day of the follow-up	
		visit.	
		VISIT.	
		* Note: In the event a lens is lost or	
		damaged, the subject will return to the	
		clinical site for replacement. As much as	
		reasonably possible, a damaged lens and	
		packaging should be returned to the clinical	
		site (wet, if possible) and then returned to the	
		Sponsor. If lens damage is present, complete	
		the Product Quality Complaint Form. The	

Visit 1: Treatment 1 Lens Fitting				
Step	Procedure	Details		
		lens will be stored in labeled vial with saline,		
		and clearly differentiated from the other worn		
		lenses that will be shipped back to the		
		Sponsor.		

VISIT 2

The subjects must present to Visit 2 wearing the study lenses and having worn them continuously for at least six (6) hours on the day of the visit immediately prior to attending the visit.

	Visit 2: Treatment 1 Follow-Up 1			
Step	Procedure	Details		
2.1	Adverse Events and Concomitant Medications Review	Review any changes to the subject's medical history or concomitant medications from the previous study visit. Record any changes, and any adverse events.		
2.2	Wearing Time	Record the average wearing time and comfortable wearing time.		
2.3	Compliance	Confirm compliance with the prescribed wear schedule.		
2.4	Subject Reported Ocular Symptoms	Subjects will respond to a verbal open-ended symptoms questionnaire.		
2.5	CLUE Follow-Up Questionnaire	The subject will respond to the CLUE Follow-Up Questionnaire		
2.6	Visual Acuity	Record the distance Snellen visual acuity with the contact lenses (OD, OS and OU) to the nearest letter. Subjects must read the smallest line until at least 50% of the letters are read incorrectly.		
2.7	Cosmetic Lens Fit Assessment (without slit-lamp)	The Cosmetic Lens Assessment will be assessed by the investigator (without slit- lamp) in primary gaze and extreme gaze (right, left, and upgaze) at a normal conversation distance (approximately three (3) feet away from the subject).	Appendix E	
2.8	Hula Hoop Assessment (without slit-lamp) *If unacceptable cosmetic fit in any gaze.*	If there is an unacceptable cosmetic fit in any gaze, the Hula Hoop Assessment will be assessed by the investigator (without slit- lamp) in primary gaze and extreme gaze (right, left, and upgaze) at a normal conversation distance (approximately three (3) feet away from the subject).	Appendix E	

	I	visit 2: Treatment 1 Follow-Up 1	
Step	Procedure	Details	
2.9	Subjective Lens Fit Assessment	 Evaluate overall lens fit acceptance (acceptable or unacceptable) based on centration, movement and other fitting characteristics. An unacceptable fit is deemed by one of the following criteria: limbal exposure at primary gaze or with extreme eye movement. edge lift. excessive movement in primary and up gaze. insufficient movement in all three of the following conditions: primary gaze, up gaze, and push-up test. Note: if lens fit is unacceptable subject will be discontinued from the study. 	
2.10	Wettability Characteristics	Record the white light lens wettability of both lenses.	
2.11	Surface Deposits	Record any front and back surface lens deposits.	
2.12	Remove lenses	The lenses will be removed and discarded.	
2.13	Slit Lamp Biomicroscopy	FDA Slit Lamp Classification Scale will be used to grade the findings.	
		If the subject has a Grade 3 slit lamp finding, it will be recorded as an Adverse Event and the subject will be monitored as per the guidelines given in section 13. If the clearance of the fluorescein needs to be expedited, preservative-free rewetting drops may be instilled.	
2.14	Washout instructions	Subjects are instructed to wear their spectacles or habitual contact lenses for 2-5 days.	
2.15	Exit VA	Record the distance Snellen visual acuity (OD, OS, and OU) to the nearest letter with their habitual spectacles (where applicable). Subjects must read the smallest line until at least 50% of the letters are read incorrectly.	

VISIT 3

The subjects must present to Visit 3 not wearing their habitual contact lenses.

	Visit 3: Treatment 2 Treatment		
Step	Procedure	Details	
3.1	Adverse Events and Concomitant Medications Review	Review any changes to the subject's medical history or concomitant medications from the previous study visit. Record any changes, and any adverse events.	
3.2	Visual Acuity	Record the distance Snellen visual acuity with the contact lenses (OD, OS and OU) to the nearest letter. Subjects must read the smallest line until at least 50% of the letters are read incorrectly.	
3.3	Slit Lamp Biomicroscopy	FDA Slit Lamp Classification Scale will be used to grade the findings. If the subject has a Grade 3 slit lamp finding, it will be recorded as an Adverse Event and the	
		subject will be monitored as per the guidelines given in section 13. If the clearance of the fluorescein needs to be expedited, preservative-free rewetting drops may be instilled.	
3.4	Continuance	Confirm the subject is able to continue in the study.	
3.5	Lens Selection	Assign the study lens based on the lens fitting schedule. Select the contact lens power based on subjective best sphere refraction.	
3.6	Lens Insertion	The Subject inserts the study lenses. Record the time of lens insertion. Check for lens damage under the slit lamp before proceeding with lens settling. Replace damaged lenses if applicable.	
3.7	Lens Settling	Allow the study lenses to settle for a minimum of 5 minutes.	
3.8	Subjective Best Sphere Over Refraction	Perform subjective best sphere refraction over the study lenses with a phoropter (adopt the maximum plus to maximum visual acuity (MPMVA) approach and use the duo-chrome	

	· · · · · · · · · · · · · · · · · · ·	Visit 3: Treatment 2 Treatment	
Step	Procedure	Details	
		test for binocular balancing) and record the best corrected distance visual acuity to the nearest letter (OD, OS, OU).	
		Note: The endpoint criterion for the duo- chrome test is the lens power at which the red and green sides of the chart appear to be equally distinct. However, if the subject's response changes from "red" to "green" with only a 0.25D change in power and no report that the two sides appear to be equally sharp, the refraction endpoint should be the lens power that leaves the red chart sharper.	
3.9	Lens Power Modification (if applicable)	Adjust the lens power if the subject's best sphere over-refraction is not plano. For each power modification, repeat steps (3.7- 3.9). Two power modifications are allowed.	
3.10	Visual Acuity	Record the distance Snellen visual acuity (OD, OS, and OU) to the nearest letter with the study contact lens correction in place. Subjects must read the smallest line until at least 50% of the letters are read incorrectly.	
3.11	Distance ETDRS logMAR Visual Acuity	Per , please confirm room illuminance and chart luminance	
		 Under high illumination and high chart luminance, record the distance (4 meter) ETDRS low contrast visual acuity twice OD (LC1-LC2) and twice OS (LC3-LC4). With the goggles on, under normal illumination and chart luminance, record the distance (4 meter) ETDRS high contrast visual acuity twice OD (HC5- HC6 and twice OS (HC7-HC8). Allow 	
Visit 3: Treatment 2 Treatment			
--------------------------------	--	--	---------------
Step	Procedure	Details	
		subject to adjust to dim condition for 3 minutes.	
		Letter-by-letter results will be recorded into the electronic data capture form, which will calculate the visual performance score for each	
		chart read.	
3.12	Subject Reported Ocular Symptoms	Subjects will respond to a verbal open-ended symptoms questionnaire.	
3.13	CLUE Post-Fit Questionnaire	The subject will respond to the CLUE Post-Fit Questionnaire	Appendix A
	Cosmetic Lens Fit Assessment (without slit- lamp)	The Cosmetic Lens Assessment will be assessed by the investigator (without slit-lamp) in primary gaze and extreme gaze (right, left, and upgaze) at a normal conversation distance (approximately three (3) feet away from the subject).	Appendix E
3.15	Hula Hoop Assessment (without slit- lamp) *If unacceptable cosmetic fit in any gaze.*	If there is an unacceptable cosmetic fit in any gaze, the Hula Hoop Assessment will be assessed by the investigator (without slit-lamp) in primary gaze and extreme gaze (right, left, and upgaze) at a normal conversation distance (approximately three (3) feet away from the subject).	
3.16		 Evaluate overall lens fit acceptance (acceptable or unacceptable) based on centration, movement and other fitting characteristics. An unacceptable fit is deemed by one of the following criteria: limbal exposure at primary gaze or with extreme eye movement. edge lift. excessive movement in primary and up gaze. insufficient movement in all three of the following conditions: primary gaze, up gaze, and push-up test. 	

Visit 3: Treatment 2 Treatment			
Step	Procedure	Details	
350		Note: if lens fit is unacceptable subject will be	
		discontinued from the study.	
3.17	Wettability	Record the white light lens wettability of both	
	Characteristics	lenses.	
3.18	And a second sec	Record any front and back surface lens	
	Deposits	deposits.	
3.19	Continuance	For the subject to continue in the study, they	
		must meet all three of the following criteria:	
		 Visual acuity is 20/30 or better OD and OS 	
		• The lens fit is acceptable OD and OS	
		• Investigator approval. If the	
		Investigator does not approve the	
		dispensing of the first study lens, then	
		the study is terminated for that subject.	
		 Subject is willing to wear the lenses for 	
		the dispensing period for 6 hours per	
		day and will not wear their habitual	
		lenses during the dispensing period.	
3.20	Dispense	The lenses will be dispensed for a 5 to 7 day	
		wearing period. During this time, they are	
		required to wear the lenses at least 6 hours per	
		day.	
		 Dispense enough lenses to last the 	
		subject to their scheduled follow-up	
		visit. Do not dispense extras*.	
		• The lenses will be worn as daily	
		wear/daily disposable only.	
		• Rewetting drops are permitted if needed.	
		 A patient instruction booklet will be provided 	
		provided.	
		 Subjects will be scheduled for their 5-7- day follow up visit anywing that they 	
		day follow-up visit, ensuring that they wear the study lens at least 6 hours on	
		the day of the follow-up visit.	
		are day of the follow up visit.	
		* Note: In the event a lens is lost or damaged,	
		the subject will return to the clinical site for	
		replacement. As much as reasonably possible, a	
		damaged lens and packaging should be returned	
		to the clinical site (wet, if possible) and then	
		returned to the Sponsor. If lens damage is	
		present, complete the Product Quality	

	Visit 3: Treatment 2 Treatment		
Step	Step Procedure Details		
		Complaint Form. The lens will be stored in	
	labeled vial with saline, and clearly differentiated from the other worn lenses that		
		will be shipped back to the Sponsor.	

VISIT 4

The subjects must present to Visit 4 wearing test article for at least six (6) hours on the day of the visit.

	Visit 4: Treatment 2 Follow-Up			
Step	Procedure	Details		
4.1	Adverse Events and	Review any changes to the subject's medical		
	Concomitant	history or concomitant medications from the		
	Medications Review	previous study visit. Record any changes,		
		and any adverse events.		
4.1	Wearing Time	Record the average wearing time and		
		comfortable wearing time.		
4.2	Compliance	Confirm compliance with the prescribed		
	A 1 1 3 7 5 1	wear schedule.		
4.3	Subject Reported	Subjects will respond to a verbal open-ended		
	Ocular Symptoms	symptoms questionnaire.		
4.4	CLUE Follow-Up	The subject will respond to the CLUE		
	Questionnaire	Follow-Up Questionnaire	n	
4.5	Preference questions			
		Follow-Up Questionnaire		
4.6	Entrance Visual	Record the distance Snellen visual acuity		
	Acuity	(OD, OS, and OU) to the nearest letter with		
		study contact lens in place. Subjects must		
		read the smallest line until at least 50% of		
		the letters are read incorrectly.		
4.7	Cosmetic Lens Fit	The Cosmetic Lens Assessment will be	Appendix	
	Assessment	assessed by the investigator (without slit-	E	
	(without slit-lamp)	lamp) in primary gaze and extreme gaze		
		(right, left, and upgaze) at a normal		
		conversation distance (approximately three		

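### The movement rule for an unacceptable lens fit at Visit 1 (step 1.28) differs from the rule at Visits 2 to 4: wrong as written, low impact

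*Combined protocol and SAP*

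**What the plan says.** All four fit assessments in protocol section 7.2 list limbal exposure, edge lift and a movement criterion, and each says that an unacceptable fit ends the subject's participation. The movement criterion is worded in two ways.

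- **Visit 1, step 1.28.** The lens fails for "Presence of unacceptable movement (excessive or insufficient) in" all three "of the following conditions: primary gaze, up gaze, and tightness on push up". Excessive and insufficient movement share this one threshold.
- **Visits 2, 3 and 4, steps 2.9, 3.16 and 4.9.** The criterion is split. The lens fails for "excessive movement in primary and up gaze", with no push-up condition. Insufficient movement must be present in primary gaze, up gaze and push-up together. The three steps are worded alike.

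Visits 1 and 3 are both fitting visits. Each has the instruction "Allow the study lenses to settle for a minimum of 5 minutes" (steps 1.19 and 3.7), and each makes dispensing depend on an acceptable fit and on the investigator's agreement (steps 1.31 and 3.19).

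Section 2.2 lists mechanical lens fit among the exploratory endpoints. Section 14.1 plans summaries by lens type and timepoint, with a single Fitting Evaluation timepoint. Sections 14.6 and 14.7 are marked as not applicable.

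**The concern.** A criterion that decides who stays in the study should be the same wherever the same check is made, unless a reason is given. Here the two fitting visits apply different rules to one assessment. A subject could be dispensed a loose lens at Visit 1 and be discontinued at Visit 3 for the same finding in the other lens.

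Two things are at stake. One is conduct: sites must apply two discontinuation rules and the eCRF must carry both. The other is the meaning of the mechanical-fit endpoint. In a 2×2 crossover each lens is fitted at Visit 1 in one sequence and at Visit 3 in the other. A Fitting Evaluation table by lens would then count acceptable fits under two definitions.

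**Working it through.** No figure in the plan depends on this rule, so the check is a comparison of wording.

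**1. The case that separates the rules.** Take a lens with excessive movement in primary gaze and in up gaze, acceptable push-up, no limbal exposure and no edge lift.

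| Check | Step 1.28 (Visit 1) | Steps 2.9, 3.16, 4.9 (Visits 2–4) |
|---|---|---|
| Limbal exposure | absent: pass | absent: pass |
| Edge lift | absent: pass | absent: pass |
| Movement | unacceptable in two of three conditions: pass | excessive in both gazes: fail |
| Fit | acceptable | unacceptable, discontinue |

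This does not depend on whether step 1.28 requires the same direction of movement in all three conditions or allows a mix. Push-up is acceptable, so the three-condition threshold is not met on either reading.

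**2. Insufficient movement.** A lens with insufficient movement in all three conditions fails under both rules, so the rules agree there. On a literal reading, step 1.28 would also fail some lenses that combine excessive movement in one condition with insufficient movement in another, which the later rule passes. Those are contradictory signs and unlikely to matter.

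**3. Could fitting versus follow-up explain it?** No. Visit 3 is a fitting visit with the same minimum settling time, but it uses the follow-up wording.

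**4. Effect on the fit summary.** Assume that the Fitting Evaluation table pools Visits 1 and 3, which section 14.1 implies but does not state, and that the sequences are about equal in size. Roughly half of each lens's fittings then fall under each rule. Because sequence is randomised (section 5.1), both lenses are exposed to both rules.

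**5. Effect on the primary endpoint.** LogMAR acuity is measured before the fit check at both fitting visits (1.23 before 1.28; 3.11 before 3.16), so a failed fit does not remove that visit's acuity. A Test-first subject has already given Test acuity. A Control-first subject discontinued for fit at Visit 1 or Visit 2 never gives it, and section 14.9 does not impute.

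- Planned Test eyes: 46 completers × 2 = 92.
- Loss per unreplaced Control-first subject: 2 / 92 = 2.2%.
- Enrolment allowance: 60 − 46 = 14 subjects. Section 8.2 also provides for further enrolment after a discontinuation.

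The documents give no rate of excessive movement, so the number of such subjects cannot be estimated.

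**The case against.** The strongest reply is that very few lenses will be caught between the two rules. The lens must be loose in two gazes and still show neither limbal exposure nor edge lift. The package insert (Appendix C) groups those signs with excessive movement as marks of a flat fit, so they will often occur together. Step 1.18 adds a safeguard at insertion, "If the lens moves excessively on the eye after insertion, ask the subject to remove the lens, confirm lens is not inverted", and the investigator can refuse to dispense at step 1.31. Lens fit has no planned inferential analysis. All of this stands, and it is why the point is minor. It does not make the two texts agree.

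A second reply is that the lens-fitting procedure in Appendix F, blacked out in the public copy, may settle the matter. It may. Section 7.2 would still carry two conflicting rules.

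A reader might infer more than the documents support:

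- **That the comparison of lenses is biased.** The difference follows the visit, and randomised sequence places each lens at both fitting visits.
- **That the primary result is at risk.** The only loss is of whole Control-first subjects before Visit 3, and they can be replaced.
- **That a subject passed at Visit 1 will fail at Visit 2.** These are daily disposables. The lens seen at Visit 2 is a different one, assessed after "having worn them continuously for at least six (6) hours on the day of the visit", so the finding need not recur.
- **That the number of affected movement patterns measures the problem.** Such a count would need the push-up grading scale, which is not visible, and would say nothing about how many subjects are affected.

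**Conclusion.** The point holds as a minor correction. The movement criterion that triggers discontinuation is inconsistent between step 1.28 and steps 2.9, 3.16 and 4.9, and the visible text does not explain why the two fitting visits differ. The definite consequence is one kind of loose lens that passes the fit criteria at Visit 1 and fails them at Visit 3.

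The effect on results is small. A pooled Fitting Evaluation summary would mix two definitions of an acceptable fit, in an exploratory endpoint that is only described. There is no systematic bias between lenses, and the effect on the primary endpoint is negligible. The size in subjects is unknown.

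This rests on the section 7.2 wording as published, on pooling of Visits 1 and 3 for the summary, and on Appendix F not already overriding step 1.28.

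**What to change.** Replace the movement bullet in step 1.28 with the two bullets used at Visits 2 to 4: one failing the lens for "excessive movement in primary and up gaze", and one failing it for insufficient movement only when that is seen in primary gaze, up gaze and push-up alike. Put the same text in the eCRF. Before doing so, the sponsor should confirm the clinical choice and check it against the Appendix F lens-fitting procedure. The later wording is a sensible default because the package insert lists excessive movement as a sign of a flat fit and, as far as its broken text can be read, says such a lens should not be dispensed.

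The cost is a small protocol and eCRF edit, with no added procedure. Visit 1 becomes slightly stricter for loose lenses, so a few more subjects may be discontinued there, including some who would have continued because the finding would not have recurred at Visit 2. A Control-first subject stopped at Visit 1 gives no Test acuity, and a Test-first subject stopped there gives no further Control data. The change makes the rule and the fit summary consistent; it does not itself preserve Test acuity data.
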